6.1. General Considerations

All statistical analyses will be performed using Statistical Analysis Software (SAS) for Windows (version 9.1 or higher) or other widely accepted statistical or graphical software. Subject data listings and tabular and graphical presentations of results will be provided.

All analyses will be based on “intent to treat” (ITT) principle, unless otherwise specified. For clinical events, the numerator of the event rate will be the number of “ITT” subjects having an event before the time of interest. The denominator will be the number of subjects who either have an event by the time of interest, or have follow-up information beyond the lower window of the follow-up.

The Clinical Study Report will be available for the primary endpoint (12 months) and for secondary endpoints annually through study close-out at 3 years.

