4.4 Subject Selection

All subjects presenting to the cardiac catheterization laboratory for possible interventional treatment are potential candidates. Those subjects who sign the Institutional Review Board (IRB) approved informed consent and subsequently fulfill all inclusion criteria and no exclusion criteria will be enrolled in the trial.

RESOLUTE Onyx 2.0 mm Clinical Study**CONFIDENTIAL - May not be reproduced without written permission from Medtronic**

Screening of candidates for this trial should include assessment of the need for anticipated treatment of other target vessel lesions likely to be needed within 12 months post-procedure. Candidates in whom it is likely that other obstructive lesions will require treatment within the target vessel(s) within 12 months post-procedure should not be enrolled in this trial, as assessment of key safety endpoints will occur at 12 months post-procedure.

Per intent-to-treat principles (ITT), subjects who did not have a study stent (Resolute Onyx 2.0 mm stent) implanted but a study stent was introduced into the guide catheter will be followed through 12 months.

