5.4.6 Treatment Failure

Following subject enrollment, study stent(s) that enter the guide catheter and fail to be implanted at the intended location are considered treatment failures and will be recorded in the eCRF. In the event of a failure to implant at least one study stent, the Investigator may choose to treat the target lesion(s) with any approved stent. Treatment failures will be followed-up for safety purposes through 12-months and will be included in the intent-to-treat (ITT) population. The subject will undergo the follow-up assessments listed in [Section 5.6](#) through the 12 month follow-up assessment.

Note: Damaged or failed Resolute Onyx Stent Systems (including ancillary devices) must be returned to the Medtronic Product Experience Management Department per instructions provided by Medtronic.

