5.6 Follow-Up Requirements

5.6.1 Follow-up General Requirements

The general requirements for follow-up in this trial include:

1. Enrolled subjects who received a study stent will be followed for 3 years after the index procedure by authorized study staff at the investigational site. See [Table 6](#) for follow-up assessment requirements.
2. Subjects in the 2.0 mm Angio subset will return to the site where the procedure was performed for a 13-month clinic visit including an angiogram. Other follow-up contacts will be conducted by telephone, e-mail or clinical visit, unless an unscheduled clinic visit occurs during a follow-up window.
3. A missed follow-up assessment will be documented by the investigator and reported in the eCRF, including the reason for the missed follow-up assessment in the subject's file.
4. Clinical assessments (e.g., angina status, use of antiplatelet medication, new and ongoing adverse events; medical, surgical or dental procedures and the interruption, if any, to antiplatelet therapy) must be performed at each follow-up contact and prior to any interventional procedure (e.g., angiography, PCI) during the 3-year follow-up period.
5. Documentation of referring physicians, general practitioners, cardiologists and family members should be noted to facilitate continued ability to contact a study subject. Any planned long absences by the subject from the area should also be noted.
6. Angiography should be performed for any post-procedure clinical event (e.g., MI) to determine if the event is attributable to the target vessel(s) or a non-target vessel.

The schedule and method for follow-up contacts and windows for each contact is tabled below.

Table 6: Follow-up Contact Requirements

Follow-up Interval	Window	Method*
30 days	± 5 days	Contact
6 months	±14 days	Contact/Clinic Visit**
12 months	± 30 days	Contact
12 month Clinical Follow up must occur at least 1 day prior to the 13 month Angiographic Follow up		
13 months (2.0 mm Angio subset)	± 14 days	Clinic Visit (with Angio)
2 Year	± 30 days	Contact
3 Year	± 30 days	Contact

*Subject contact includes phone call, email or clinic visit

**Clinic visit for subjects with baseline MPI performed, otherwise subject contact visit

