3.1. Treatment(s) and Subject Enrollment

At least 100 subjects with ischemic heart disease due to *de novo* stenotic lesions within native coronary arteries that meet the eligibility criteria and sign the informed consent form will be asked to participate in this trial. All subjects who consent will be asked to participate in the 13 month angiographic subset until at least 20 subjects have been enrolled in this subset. Subjects may receive treatment in up to two lesions, if the lesions are located in separate target vessels. Only one lesion may be treated in a single target vessel. Core size lesions should be treated with the currently approved Resolute Integrity stent. All treatment with the study stents is to be performed during a single index procedure.

In the event of one lesion to be treated with a 2.0 mm study stent and another lesion to be treated with a core size (2.25 mm - 4.0 mm) Resolute Integrity stent, the subject should be treated first with the core-sized stent. If the treatment of the first lesion fails or if the subject becomes unstable before a 2.0 mm study stent is attempted (stent introduced into guide catheter), the subject will not be enrolled, will not be followed, and will not be included in the primary analysis of this trial. Another subject should be enrolled to replace this subject for the primary analysis. If the treatment with the 2.0 mm study stent is attempted (stent introduced into guide catheter) but not implanted, the subject will be considered part of the Intention-to-Treat population (ITT) and will be followed through the 12 month endpoint and will be included in the primary analysis of this trial.

For subjects who have more than one lesion planned for treatment, FFR should be performed in the vessel expected to receive the 2.0 mm study stent to demonstrate the functional need for treating such a lesion, unless demonstrated by other means (clinical evidence and/or positive functional study).

The trial will be conducted at a maximum of 25 investigational sites within the United States (US) and Japan. Sites are allowed to enroll a maximum of 20 subjects per site or until study enrollment has been completed, whichever comes first. The expected time of participation in the trial for each subject is three years.

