3.2.2. Key Secondary Endpoints

Secondary endpoints of this trial include the following:

Clinical Endpoints:

- Acute Success (Device, Lesion, Procedure)
- The following secondary endpoints will be assessed at hospital discharge, 30 days, 6 months, and 12 months post-procedure, and annually thereafter through year 3:
 - Cardiac Death
 - Target Vessel Myocardial Infarction (TVMI)
 - Cardiac Death and TVMI
 - Target Lesion Revascularization (TLR)
 - Major Adverse Cardiac Event (MACE)
Defined as death, myocardial infarction (Q wave and non-Q wave), emergent coronary bypass surgery, or clinically-driven repeat target lesion revascularization by percutaneous or surgical methods
 - Target Lesion Failure (TLF)
 - Target Vessel Failure (TVF)
 - Stent Thrombosis (ST)

Imaging Endpoint:

- The following secondary endpoint will be assessed at 6 months for subjects who received Myocardial Perfusion Imaging (MPI) per standard care at baseline:
 - Percentage of Myocardium with Reversible Ischemia per Myocardial Perfusion Imaging

Other clinical parameters of stress testing will be collected at baseline and at follow-up testing to assess change following the stenting procedure. These parameters include stress induced angina symptoms, incidence of ST-depression, and exercise capacity.

Angiographic Endpoints:

- The following Angiographic Endpoints will be assessed at 13 months post-procedure (for at least 20 patients):
 - Late Lumen Loss (LL)
 - Binary Angiographic Restenosis (BAR) rate (defined as >50% diameter stenosis (DS))
 - Percent Diameter Stenosis

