3.4. Analysis Strategy

Descriptive statistics will be presented for this study. Hypothesis testing with performance goal will be evaluated for primary endpoint.

4. Analysis Populations

Intent-to-Treat (ITT): For this trial, all subjects who sign the written informed consent and also have the study stent (Resolute Onyx 2.0 mm stent) introduced into the guide catheter will be counted in the ITT set, which will be the primary analysis set.

Per-Protocol (PP): The ITT population excluding subjects who do not meet certain key entry criteria (for exclusion criteria below, if any answer is “yes”, the subjects are excluded from PP population):

1. Did not receive any study device
2. Received study device, and another type of DES
3. Did not meet the following inclusion criteria:
 - a. General Inclusion 3: Subject has clinical evidence of ischemic heart disease, For single vessel disease: stable or unstable angina alone is sufficient. For multi-vessel treatment: a positive functional study or FFR to demonstrate functional need in 2.0 mm small vessel.
 - b. Angiographic Inclusion 1: The subject requires treatment of either:
 - i. A single target lesion amenable to treatment with a 2.0 mm stent
 - OR
 - ii. Two target lesions located in separate target vessels, with at least one of the target lesions amenable to treatment with a 2.0 mm study stent

- c. Angiographic inclusion 2: Target lesion(s) must be de novo lesion(s) in native coronary artery(ies)
4. Did not meet the following exclusion criteria:
- a. General exclusion 5: Evidence of an acute MI within 72 hours of the trial procedure:
 - a) Q wave myocardial infarction (QWMI)
 - OR
 - b) Elevated cardiac biomarker values [preferably cardiac troponin (cTn)] with at least one value above the upper reference limit (URL) and with at least one of the following:
 - Symptoms of ischemia
 - New or presumed new significant ST-segment–T wave (ST–T) changes or new left bundle branch block (LBBB)
 - Development of pathological Q waves in the ECG
 - Imaging evidence of new loss of viable myocardium or new regional wall

Note: Subjects with evidence or suspicion of an acute MI (per Investigator or Sub-Investigator determination) must have cardiac enzyme results reviewed prior to enrollment.
 - b. General exclusion 7: Planned PCI of any vessel within 30 days post-index procedure and/or planned PCI of the target vessel(s) within 12 months post-procedure. (no staged procedures)

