6.2. Analysis of the Primary Endpoint

The number and percentage of subjects with 12-month TLF will be presented. A one-sided upper 95% confidence interval of the Resolute Onyx 2.0 mm stent 12-month TLF rate will be calculated through binomial (exact) method. If this upper limit is below 19%, the clinical objective will be considered to have been met.

With regard to clinical outcomes analysis, in subjects receiving treatment of two lesions with a Resolute Onyx 2.0 mm stent, the lesion to be included in the primary analysis, the “analysis lesion”, will be randomly selected at the time of analysis. For subjects receiving treatment of a Resolute Onyx 2.0 mm stent and another size stent, the primary analysis will include the lesion treated with the 2.0 mm stent, regardless of the other stent size. A secondary analysis will be conducted for all target lesions.

The algorithm to randomly select the “analysis lesion” is specified below:

The seed of the ranuni function will be specified in the statistical analysis plan prior to the database lock and will not be changed. Therefore, bias cannot be introduced in the random selection of the lesion in the primary analysis.

A random lesion will be chosen for the primary analysis as follows:

1. Sort the lesions according to patient number and CASS site (with one observation per patient/CASS).
2. Assign a random number to each observation using the SAS ranuni function (the seed will be pre-specified in the statistical analysis plan).
3. Resort the lesions according to patient number and newly created random number.
4. Choose the first patient/CASS observation according to the sort in step 3.

As a supplementary analysis, to account for missing data, subjects who drop out prior to 330 days post-procedure and do not experience TLF will have their 12-month TLF-free status (yes/no) imputed using the multiple imputation, tipping point analysis and worst case analysis.

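### Under the SAP 6.1 denominator, ITT subjects who never received the study stent appear to count at 24 and 36 months only if they had an event, and early non-cardiac deaths drop out of the 12-month TLF rate (minor)

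*SAP*

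**What the plan says.** **Denominator.** Analyses are ITT unless otherwise specified. SAP 6.1 puts ITT subjects with an event in the numerator, and in the denominator "subjects who either have an event by the time of interest, or have follow-up information beyond the lower window of the follow-up". ITT requires consent and a study stent introduced into the guide catheter (SAP 4); implantation is not required.

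**Follow-up of subjects never implanted.** SAP 3.1 says that such a subject "will be considered part of the Intention-to-Treat population (ITT) and will be followed through the 12 month endpoint". Protocol 4.4 says that subjects without an implanted study stent "but a study stent was introduced into the guide catheter will be followed through 12 months". Protocol 5.4.6 adds: "Treatment failures will be followed-up for safety purposes through 12-months and will be included in the intent-to-treat (ITT) population". Protocol 5.6.1 ties the longer follow-up to implantation: "Enrolled subjects who received a study stent will be followed for 3 years after the index procedure".

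**Text that points the other way.** Protocol 1.7 lists the 2- and 3-year contacts for all subjects. Protocol 1.6 and SAP 3.1 give three years as each subject's expected participation. Protocol Table 3 shows the 24- and 36-month contacts with no exception for failed implants.

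**Reporting times.** The secondary clinical endpoints are assessed at discharge, 30 days, 6 months and "12 months post-procedure, and annually thereafter through year 3". SAP Appendix II sets the windows at 360, 720 and 1080 days, each ±30.

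**Deaths and missing data.** TLF counts cardiac death only (SAP 3.2.1), and deaths are cardiac by default unless a non-cardiac cause is unequivocal (Protocol Appendix 2). In SAP 6.2, "subjects who drop out prior to 330 days post-procedure and do not experience TLF will have their 12-month TLF-free status (yes/no) imputed" by multiple imputation, tipping-point and worst-case methods. The SAP does not say whether death counts as dropping out.

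**The concern.** A subject normally belongs in a rate's denominator because he or she was observed long enough, whatever the outcome. Under SAP 6.1 combined with the 12-month follow-up rule, a never-implanted subject is kept at 24 and 36 months if an event occurred and removed if it did not. Inclusion then depends on outcome, and it does so through the planned schedule rather than chance loss. The later ITT rates for TLF and the other secondary clinical endpoints would run high, more so with more failed implants.

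No other rule clearly repairs this. The Kaplan-Meier display in SAP 6.3 is optional, the censoring rule in SAP 6.5 concerns drop-outs in time-to-event outcomes, and the imputation in SAP 6.2 covers 12-month TLF only.

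The same wording also touches the primary analysis. A subject who dies of an unequivocal non-cardiac cause before day 330 without TLF has neither an event nor follow-up past the lower window, and so leaves the denominator although the 12-month TLF status is known.

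**Working it through.** The plan gives no figure for the effect of this rule. The only plan figures used are the 19% goal, the exact one-sided 95% upper limit and the assumed 9.4% TLF rate.

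**1. Can a never-implanted subject qualify late?** Planned follow-up closes at day 360 + 30 = 390 (SAP Appendix II), or day 395 by the example in Protocol Table 7 (5 December 2014 to 4 January 2016). The later windows open at 720 − 30 = 690 and 1080 − 30 = 1050. Without incidental later data, only an event admits such a subject.

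**2. Size at 36 months.** Let u be the number never implanted per 100, q their 12-month TLF rate, and p the 36-month rate in implanted subjects, whose 12-month rate is 0.094. Everyone else is fully followed and there are no competing deaths. The documents do not give u, q or p; these are assumptions.

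- SAP 6.1 rate = [(100 − u)p + uq] / [(100 − u) + uq]
- Censored rate = 1 − {1 − [(100 − u)·0.094 + uq]/100} × (1 − p)/0.906

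| u | SAP vs censored, p = 0.15, q = 0.094 | SAP vs censored, p = 0.15, q = 0.20 | Excess in points, p = 0.10 to 0.25, both q |
|---|---|---|---|
| 2 | 15.16% vs 15.00% | 15.35% vs 15.20% | 0.13 to 0.17 |
| 5 | 15.42% vs 15.00% | 15.89% vs 15.50% | 0.34 to 0.44 |
| 10 | 15.88% vs 15.00% | 16.85% vs 15.99% | 0.75 to 0.93 |

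The sampling standard error at 15% with n = 100 is √(0.15 × 0.85/100) = 3.6 points.

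Worked example: 5 never implanted (1 TLF) and 95 implanted (9 TLF by 12 months, 14 by 36).

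- SAP 6.1: 15/96 = 15.6%
- Censored: 1 − (1 − 10/100)(1 − 5/86) = 15.2%, where 86 = 95 − 9 implanted subjects remain at risk
- Implanted only: 14/95 = 14.7%

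**3. Non-cardiac death in the primary analysis.** I removed one or two non-events at every n from 90 to 100 and every event count, and recomputed the Clopper-Pearson upper limit.

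- One removed: success becomes failure only at 11/93 (18.82%, to 11/92 at 19.01%) and 12/99 (18.90%, to 12/98 at 19.08%).
- Two removed: the same two, plus 11/94 (18.63%, to 11/92 at 19.01%) and 12/100 (18.72%, to 12/98 at 19.08%).
- At a true rate of 9.4%, the exact event count needed has probability 0.077 to 0.092, given that the deaths occur and n takes that value. The unconditional chance is smaller.

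Removing non-events can only raise the upper limit, so this cannot produce a false success.

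**4. The same death in the worst-case analysis.** If the death were treated as a drop-out and imputed as TLF, with no other missing data, 10/91 (upper limit 17.9%, success) would become 11/91 (19.2%, failure). One such flip exists at every n from 90 to 100, always at the largest passing count: 10 for n = 90 to 92, 11 for n = 93 to 98, 12 for n = 99 and 100. The probability of that count at 9.4% is about 0.08 to 0.12, again given one such death.

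**The case against.** **The premise is contested within the documents.** Protocol 1.6, 1.7 and Table 3 and one sentence of SAP 3.1 imply three years' follow-up for everyone. This stands as a limit on confidence. The specific rules in Protocol 4.4, 5.4.6 and 5.6.1, and the treatment-failure sentence in SAP 3.1, address these subjects directly and probably govern, but the conflict is real.

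**No decision depends on the later rates.** This also stands. SAP 3.4 confines testing to the primary endpoint: "Hypothesis testing with performance goal will be evaluated for primary endpoint". The excess is well below the standard error, and SAP 6.5 requires the number analysed to be reported, so a shrunken denominator would be visible.

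**Never-implanted subjects are only one instance.** True: the rule acts in the same direction on ordinary losses to follow-up. The figures above isolate one planned source and do not measure the total error in a reported rate.

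**Non-cardiac deaths are a wording matter.** Largely so. The imputation is introduced for missing data, and the natural reading is that a death with known TLF status is not missing. That reading does not cure the literal denominator in 6.1.

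A reader might infer that the primary result is biased, or biased in the device's favour. The documents do not support either reading: never-implanted subjects are followed to 12 months and stay in the primary analysis, and both effects raise the reported rates. A reader might also infer that one or two deaths are harmless at all other counts; that is true of the primary analysis but not of a worst-case analysis that treated them as missing.

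**Conclusion.** The point holds as a minor one, with moderate confidence.

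Under the specific follow-up rules, SAP 6.1 overstates the 24- and 36-month ITT rates. At 36 months the excess is about 0.1 to 0.9 point, for an assumed 2 to 10 never-implanted subjects per 100 with everyone else fully followed. If all ITT subjects are in fact followed for three years, this part falls away.

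Read literally, SAP 6.1 also drops early non-cardiac deaths from the 12-month TLF denominator. That effect is conservative, should be rare given the cardiac default, and changes the primary conclusion only at the few counts listed. The worst-case analysis is more exposed, but only if SAP 6.2 is read to make such a death a drop-out, which it does not say.

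**What to change.** **(a) SAP 6.1 and 6.3.** Reconcile the follow-up sections first. If never-implanted subjects are followed only to 12 months, report the 24- and 36-month ITT rates as cumulative-incidence estimates with numbers at risk. Censor event-free subjects at the end of their follow-up, which for never-implanted subjects is the end of the planned 12-month follow-up. Treat non-cardiac death as a competing event for endpoints that do not include it. Ordinary Kaplan-Meier is not interchangeable here, because it censors those deaths. A simpler alternative is to restrict both numerator and denominator at those times to implanted subjects and label the rates accordingly.

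**(b) SAP 6.1 and 6.2.** State that adjudicated non-cardiac deaths before day 330 without TLF stay in the 12-month TLF denominator as non-events, and are not missing for the multiple-imputation, tipping-point and worst-case analyses.

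**Cost.** A few sentences and lines of code, best settled before database lock so that the choice cannot look driven by outcome. Data collection and the exact test against 19% are unchanged. The censored estimates rely on non-informative censoring. The implanted-only option is not full ITT and drops events in failed implants (14.7% against 15.2% in the example). Keeping non-cardiac deaths as non-events slightly lowers the reported TLF rate.

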3.3. Sample Size Justification

If the 12-month TLF rate of the Resolute Onyx 2.0 mm stent is shown to be significantly less than 19%, then the trial will be considered to have met its primary objective. In other words, the assessment of TLF is a testing with the following null and alternative hypotheses:

$$H_0: \pi \geq 19\% \text{ vs. } H_1: \pi < 19\%,$$

where π is the true Resolute Onyx 2.0 mm stent 12-month TLF rate.

The assessment of the null hypothesis will be carried out at the one-sided 0.05 level of significance. Rejection of the null hypothesis indicates the Resolute Onyx 2.0 mm stent 12-month TLF rate is significantly below 19%.

Accounting for a 10% clinical loss to follow-up and one-sided 0.05 level of significance, a sample size of 100 subjects yields more than 80% power to reject the above null hypothesis in favor of the alternative, assuming the true Resolute Onyx 2.0 mm stent 12-month TLF rate is 9.4%.

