6.5. Handling of Missing Data

Every effort will be undertaken to minimize missing data. In time-to-event outcomes drop-outs will be censored at the time of discontinuation, consistent with the Kaplan-Meier approach. Unless otherwise specified, no statistical techniques will be used to impute missing data for continuous or categorical characteristics and outcomes. The number of subjects included in each analysis will be reported so that the reader can assess the potential impact of missing data.

For the primary endpoint, a sensitivity analysis will be conducted to assess the impact of censored data and will include a worst-case analysis.

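### The stated power of more than 80% does not hold for the planned exact test (77.6% at 90 evaluable subjects), and the SAP 6.1 denominator, which biases the TLF rate slightly upward, lowers it to about 73–75%

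*SAP*

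**What the plan says.** SAP 6.1 defines event rates for clinical events. The numerator is every ITT subject with an event before the time of interest. The denominator is "subjects who either have an event by the time of interest, or have follow-up information beyond the lower window of the follow-up". SAP Appendix II sets the 12-month window at 360 ± 30 days, so the lower bound is day 330. SAP 6.2 names no other denominator for the primary endpoint. It says that the one-sided 95% upper limit "will be calculated through binomial (exact) method", and success requires that limit to be below 19%.

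SAP 3.3 states that "a sample size of 100 subjects yields more than 80% power to reject the above null hypothesis", "assuming the true Resolute Onyx 2.0 mm stent 12-month TLF rate is 9.4"%, after allowing for 10% loss to follow-up and testing at one-sided 0.05. Protocol 7.2 repeats this, and Protocol 1.8 gives the same power, significance level and loss. No section names the power formula or says when losses are expected.

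For time-to-event outcomes, SAP 6.5 says that "drop-outs will be censored at the time of discontinuation, consistent with the Kaplan-Meier approach". The primary test does not use this. Event-free drop-outs before day 330 return in SAP 6.2 only through supplementary analyses: multiple imputation with one hundred data sets, a tipping-point analysis and a worst-case analysis.

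**The concern.** Whether a drop-out is counted depends on the outcome. Take two subjects lost on day 200. The one who had already had TLF stays in numerator and denominator, and the one who had not leaves both. Drop-outs can therefore contribute failures but never successes, and the rate compared with 19% is too high.

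The trial has one pass/fail criterion and about 90 evaluable subjects, so the result can turn on one event. If the estimate is inflated and the power was computed for a different test, the sponsor's risk of missing the goal at the planned rate is larger than the under 20% that the plan implies.

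**Working it through.** **Inputs from the documents.** Goal p0 = 0.19, true rate p1 = 0.094, one-sided α = 0.05, 100 subjects, 10% loss, hence n = 90 (SAP 3.3); exact upper limit (SAP 6.2); denominator rule (SAP 6.1); lower window bound day 330 (SAP Appendix II).

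**Assumption, not in the documents.** g is the share of a drop-out's 12-month TLF risk already observed before loss. It depends on when losses and events occur. The base case is 0.5 and the range 0 to 1.

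**1. Reproducing the plan's figure.** Normal approximation with null variance:

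power = Φ[(p0 − p1 − 1.645·√(p0(1−p0)/n)) / √(p1(1−p1)/n)]

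At n = 90 the two standard errors are √(0.19×0.81/90) = 0.0414 and √(0.094×0.906/90) = 0.0308. So (0.096 − 1.645×0.0414)/0.0308 ≈ 0.91, and Φ(0.91) = 81.8%. This agrees with more than 80%. Because the plan names no formula, it is a match and not proof of how the figure was obtained.

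**2. The planned exact test, no denominator bias.** At n = 90, 10 events give an upper limit of 18.1% (success) and 11 give 19.4% (failure).
- Power = P(X ≤ 10 | 90, 0.094) = 77.6%.
- Size = P(X ≤ 10 | 90, 0.19) = 3.2%.
- With no loss, n = 100 allows 12 events and power is 85.5%.

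Exact power moves in steps: 81.7% at n = 86, 75.5% at n = 92, 83.8% at n = 93. If each subject is lost independently with probability 10%, so that the evaluable number varies around 90, the average is 78.8%.

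**3. Adding the SAP 6.1 denominator.** With drop-out probability d = 0.10:
- counted events: p1·[1 − d(1 − g)]
- removed, event-free drop-outs: d·(1 − g·p1)
- expected rate ≈ p1·[1 − d(1 − g)] / [1 − d(1 − g·p1)]

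For g = 0.5: 0.094×0.95 = 0.0893; 1 − 0.10×0.953 = 0.9047; 0.0893/0.9047 = 9.87%. Power from the exact rule, with a random number of evaluable subjects:

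| g | Expected rate | Power |
|---|---|---|
| 0 | 9.40% | 78.8% |
| 0.25 | 9.64% | 76.5% |
| 0.5 | 9.87% | 74.2% |
| 0.75 | 10.10% | 71.7% |
| 1 | 10.34% | 69.3% |

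At a fixed n = 90, g = 0.5 gives 72.7%. The rule therefore costs 77.6 − 72.7 = 4.9 points at fixed n, or 78.8 − 74.2 = 4.6 points at random n. At a true rate of 19%, size falls from 3.6% (g = 0) to 2.3% (g = 0.5).

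**4. Simulation check.** 100 subjects, 10% loss uniform over days 0–330:
- Events spread evenly: mean rate 9.8%, power 74.5%.
- 40% of events in the first 30 days: 10.0%, 73%.
- Half of events at the procedure: 10.1%, 72%.
- 40% early events, and completers' last contact spread over days 330–390: 9.8%, about 75%. A contact at day 330 counts as complete, so some late events are missed, which partly offsets the upward bias.

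**5. Kaplan-Meier on the same kind of data.** The mean estimate is 9.4%. Power is about 81–83% without a contact window (up to half of events early), using a log-log limit or an exact-type limit at the effective sample size. With the window it is about 80–81%. Simulated size at a true 19% is 3.5–4.0%.

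**The case against.** The rule is pre-specified and simple, and the exact limit guarantees size. The bias is about half a point and works against the sponsor. The plan already names the affected subjects and gives them multiple imputation, tipping-point and worst-case analyses. Protocol 5.7 also limits loss through repeated contact attempts, a recommended death-database check and record-based follow-up after withdrawal, so 10% is a planning allowance and may not be reached. All of this stands. It shows that the binomial rule can reasonably remain primary. It does not rescue the power statement, which itself assumes 10% loss.

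Three stronger readings are tempting, and the documents do not support them.
- *That the denominator rule alone takes power from above 80% to 73%.* The exact test at n = 90 already gives only 77.6%. The rule adds roughly 3–5 points to a gap that begins with the choice of formula.
- *That 73% is the trial's power.* It depends on timing that the plan does not give.
- *That the bias could produce a false success.* It lowers the type I error.

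Replacing the binomial limit with Kaplan-Meier is also a trade-off. The limit is approximate, and censoring at last contact assumes that losses are non-informative. The gain shrinks once completers are contacted across the visit window, and with no drop-out Kaplan-Meier then does slightly worse than the binomial rule.

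**Conclusion.** The point holds in two parts.

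First, the SAP 6.1 denominator depends on the outcome. It biases the 12-month TLF rate upward by about 0.3–0.6 points (9.4% to about 9.7–10.0%) at 10% evenly spread loss. The direction is conservative, so what is at risk is the point estimate and the power, not the validity of a declared success.

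Second, the stated power is wrong for the planned analysis. The exact test gives 77.6% at 90 evaluable subjects before any bias. Under the SAP 6.1 denominator it is about 73–75% if losses are evenly spread and events are not heavily clustered at the procedure. Over all values of g the range is about 69–79%, and its upper end is the case with no denominator effect at all. These figures assume 100 enrolled, 10% loss and a true rate of 9.4%. With 5% loss and g = 0.5 the power is 79.0%. Enrolling more than the minimum of 100 would also change the figures.

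**What to change.** Restate the power in SAP 3.3 and in Protocol 1.8 and 7.2: about 78% for the exact test at 90 evaluable subjects, and about 73–75% (range 69–79%) under the SAP 6.1 denominator, with the drop-out timing assumption written beside it. This changes wording only.

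Optionally, pre-specify in SAP 6.2 a Kaplan-Meier estimate of 12-month TLF, censored at last contact, with a one-sided 95% upper limit. It would be a supportive analysis next to the three missing-data analyses already planned, all of which should stay.

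If the sponsor prefers to make Kaplan-Meier primary, the SAP should state that the limit is approximate and that it assumes non-informative censoring. It should also state that the power gain at 10% loss is about 4–9 points depending on contact timing, and that about 2–4 points are lost when there is no drop-out and contacts are spread over the visit window. Either choice should be fixed before database lock.
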